## 2.0 STUDY OBJECTIVES

### 2.1 Primary Objectives

To estimate the disease control rate at four months (DCR: CR, PR or SD) after a treatment regimen of cetuximab and palbociclib in patients with refractory KRAS/NRAS/BRAF wild-type metastatic CRC in both a cohort of anti-EGFR naïve therapy patients, and a cohort of patients who might benefit from a re-challenge of anti-EGFR therapy.

### 2.2 Secondary Objectives

- 2.2.1 To estimate the overall response rate at four months (ORR: CR or PR) after a treatment regimen of cetuximab and palbociclib in patients with refractory KRAS/NRAS/BRAF wild-type metastatic CRC in both a cohort of anti-EGFR naïve therapy patients, and a cohort of patients who might benefit from a re-challenge of anti-EGFR therapy.
- 2.2.2 To estimate overall survival (OS) after a treatment regimen of cetuximab and palbociclib in patients with refractory KRAS/NRAS/BRAF wild-type metastatic CRC in both a cohort of anti-EGFR naïve therapy patients, and a cohort of patients who might benefit from a re-challenge of anti-EGFR therapy.
- 2.2.3 To estimate progression free survival (PFS) after a treatment regimen of cetuximab and palbociclib in patients with refractory KRAS/NRAS/BRAF wild-type metastatic CRC in both a cohort of anti-EGFR naïve therapy patients, and a cohort of patients who might benefit from a re-challenge of anti-EGFR therapy.
- 2.2.4 To evaluate the toxicity and safety profile of the combination of palbociclib and cetuximab in patients with refractory KRAS/NRAS/BRAF wild-type metastatic CRC

### 2.3 Exploratory Objectives

#### 2.3.1

[REDACTED]

[REDACTED]

[REDACTED]

### 3.0 Criteria for Evaluation / Study Endpoints

#### 3.1 Primary Endpoint

Four-month disease control rate, defined as complete or partial response or stable disease based on RECIST 1.1 criteria at 4 months after first dose of study drugs.

#### 3.2 Secondary Endpoints

- 3.2.1 Objective response, defined as complete or partial response based on RECIST 1.1 criteria.
- 3.2.2 Overall survival (OS), defined as time from first dose of study drug to death from any cause.
- 3.2.3 Progression-free survival (PFS), defined as time from first dose of study drug to progression or death from any cause.
- 3.2.4 Toxicity assessed per NCI CTCAE v4.03 starting on day 1 of study treatment.

#### 3.3 Exploratory Endpoints

##### 3.3.1

[REDACTED]

[REDACTED]

[REDACTED]

## 4.0 PATIENT ELIGIBILITY

In order to participate in this study a subject must meet ALL of the eligibility criteria outlined below.

### 4.1 Inclusion Criteria

- 4.1.1** Written informed consent obtained to participate in the study and HIPAA authorization for release of personal health information.
- 4.1.2** Age  $\geq$  18 years at the time of consent.
- 4.1.3** ECOG Performance Status of 0-2
- 4.1.4** Histologically-confirmed metastatic CRC
- 4.1.5** Measurable disease according to RECIST v1.1 for solid tumors.
- 4.1.6** Documented wild-type in KRAS and NRAS (codons 12, 13, 59, 61, 117, and 146) and in BRAF codon 600, based on tumor tissue taken from primary or metastatic site and tested for biomarkers
- 4.1.7** Previously treated with at least two prior regimens of systemic chemotherapy for metastatic or locally advanced, unresectable disease, including fluoropyrimidines (5-fluorouracil and/or capecitabine), oxaliplatin, and irinotecan.
  - A maintenance regimen of 5-fluorouracil or capecitabine, with or without bevacizumab, should not be counted as a separate line of treatment
  - For patients who experienced disease recurrence during or within 6 months of completion of adjuvant chemotherapy with fluoropyrimidine and oxaliplatin, only one regimen of systemic chemotherapy for metastatic disease is required
- 4.1.8** Demonstrate adequate organ function as defined in the table below; all screening labs to be obtained prior to initiating study medications.

System	Laboratory Value
Hematological*	
Hemoglobin (Hgb)	$\geq 9$ g/dL
Absolute Neutrophil Count (ANC)	$\geq 1500/\text{mm}^3$
Platelets	$\geq 100,000/\text{mm}^3$
Renal*	

Creatinine OR Calculated creatinine clearance	$\leq 1.5 \times \text{ULN}$ $\geq 60 \text{ mL/min}$ by Cockcroft-Gault formula
Hepatic*	
Bilirubin	$\leq 1.0 \times \text{upper limit of normal (ULN)}$
Aspartate aminotransferase (AST)	$\leq 3 \times \text{ULN}$ OR $\leq 5 \times \text{ULN}$ (if liver metastases present)
Alanine aminotransferase (ALT)	$\leq 3 \times \text{ULN}$ OR $\leq 5 \times \text{ULN}$ (if liver metastases present)

\*Note: Hematology and other lab parameters that are  $\leq$  grade 2 BUT still meet criteria for study entry are allowed. Furthermore, changes in laboratory parameters during the study should not be considered adverse events unless they meet criteria for dose modification(s) of study medication outlined by the protocol and/or worsen from baseline during therapy.

- 4.1.9 Females of childbearing potential must have a negative serum pregnancy test within 72 hours prior to initiating study medications. **NOTE:** Females are considered of childbearing potential unless they are surgically sterile (have undergone a hysterectomy, bilateral tubal ligation, or bilateral oophorectomy) or they are naturally postmenopausal for at least 12 consecutive months. Documentation of postmenopausal status must be provided.
- 4.1.10 Females of childbearing potential must be willing to abstain from heterosexual activity or to use 2 forms of effective methods of contraception from the time of informed consent until 6 months after treatment discontinuation. The two contraception methods can be comprised of two barrier methods, or a barrier method plus a hormonal method or an intrauterine device that meets  $<1\%$  failure rate for protection from pregnancy in the product label.
- 4.1.11 Male patients with female partners must have had a prior vasectomy or agree to use an adequate method of contraception (i.e., double barrier

method: condom plus spermicidal agent) starting with the first dose of study therapy through 6 months after the last dose of study therapy.

- 4.1.12** Subjects is willing and able to comply with study procedures based on the judgement of the investigator or protocol designee.
- 4.1.13** Able to swallow capsules, with no surgical or anatomic condition that will preclude the patient from swallowing and absorbing oral medications.
- 4.1.14** Has not undergone any major surgical procedures for at least 4 weeks, with full healing of all surgical wounds
- 4.1.15** At sites in the Southeastern U.S., subject must have negative serum test for galactose-alpha-1,3-galactose IgE. See Appendix 12.5 for map (**Note:** positive test result is predictive of immediate-onset anaphylaxis reaction during first exposure to cetuximab, which is prevalent predominantly in limited geographic region of the Southeastern U.S. (Clin Mol Allergy 2012;10:1-11)).
- 4.1.16** For Study Cohort A, has not had prior treatment with cetuximab, panitumumab, or other anti-EGFR therapy.
- 4.1.17** For Study Cohort B, must have had previous treatment with cetuximab or panitumumab with disease control (defined as complete response, partial response, or stable disease) lasting for  $\geq 4$  months in duration and completed their last anti-EGFR therapy 8 weeks prior to initiating treatment.

## **4.2 Exclusion Criteria**

- 4.2.1** Active infection requiring systemic therapy.
- 4.2.2** Pregnant or breastfeeding (NOTE: breast milk cannot be stored for future use while the mother is being treated on study).
- 4.2.3** Presence of known, active central nervous system (CNS) metastases.
- 4.2.4** Treatment with any investigational drug within 28 days prior to initiating study medications.
- 4.2.5** Prior treatment with drug targeting cyclin-dependent kinase (CDK) family.

**4.2.6** Subject is receiving prohibited medications or treatments as listed in section 5.5 of the protocol that cannot be discontinued/replaced by an alternative therapy.

**4.2.7** Known hypersensitivity to the components of study drugs or analogs of study drugs.

**4.2.8** Has a known additional malignancy that is active and/or progressive requiring treatment; exceptions include basal cell or squamous cell skin cancer, in situ cervical or bladder cancer, or other cancer for which the subject has been disease-free for at least five years.

**4.2.9** Uncontrolled, severe concomitant comorbidity (e.g. uncontrolled hypertension, uncontrolled diabetes mellitus, clinically significant pulmonary disease, clinically significant neurological disorder, active or uncontrolled infection).

**4.2.10** History of interstitial lung disease or pneumonitis.

**4.2.11** Any other clinically significant heart disease, including angina pectoris, resting bradycardia, left bundle branch block, ventricular tachyarrhythmia, unstable atrial fibrillation, acute myocardial infarction, or heart disease requiring cardiac pacemaker or implantable cardioverter/defibrillator

**4.2.12** Known psychiatric or substance abuse disorder that would interfere with the ability of the patient to comply with trial requirements.

**4.2.13** History of long-QT syndrome.

**4.2.14** Baseline QTcF  $\geq$  470 msec.

[figure not shown]
**4.2.15** Concomitant use of drugs known to cause QT prolongation as defined in Appendix 12.4 and in section 5.5 (Note: Ondansetron at doses  $\leq$  16 mg or less is allowed)

**4.2.16** History of any of the following cardiovascular conditions within the past 6 months:

- Class III or IV congestive heart failure as defined by the New York Heart Association Criteria
- Cardiac angioplasty or stenting
- Myocardial infarction
- Unstable angina
- Symptomatic peripheral vascular disease or other clinically significant cardiac disease

## 5.0 TREATMENT PLAN

### 5.1 Schema

This is a multicenter Phase II trial of palbociclib and cetuximab combination therapy in KRAS, NRAS, and BRAF wild-type metastatic CRC patients. The trial will initially enroll 22 patients stratified for enrollment into one of two cohorts (A or B) depending on their prior treatment history. Cohort A will evaluate cetuximab and palbociclib in anti-EGFR naïve patients, and Cohort B will evaluate this regimen in patients previously exposed to anti-EGFR therapy who experienced at least 4 months of disease control on their prior anti-EGFR therapy and completed their last anti-EGFR therapy at least 8 weeks prior to initiating treatment in this trial. Cohort A will initially enroll 12 patients. If  $\geq 6$  out of 12 patients experience disease control lasting  $\geq 4$  months on palbociclib and cetuximab in this cohort, then enrollment in this arm will continue and an additional 14 patients will be enrolled (n = 26). Cohort B will initially enroll 10 patients with prior exposure to anti-EGFR therapy. If  $\geq 4$  out of 10 patients experience disease control lasting for at least 4 months on palbociclib and cetuximab in this cohort, then enrollment in this arm will continue and an additional 11 patients will be enrolled (n = 21). Thus, up to 47 evaluable patients could enroll in this study if the combination demonstrates efficacy in both cohorts. Cetuximab will be given per standard of care (400 mg/m^2 IV load on cycle 1 day 1, followed by cetuximab 250 mg/m^2 IV weekly) and palbociclib 125 mg once daily (qd) on days 1-21 of a 28 day cycle, along with cetuximab until disease progression or withdrawal from study therapy for other reasons.

## 5.2 Treatment Dosage and Administration

REGIMEN DESCRIPTION					
Agent	Premedication; Precautions	Dose	Route	Schedule	Cycle Length
Palbociclib	Take palbociclib with food	125mg	oral	Once daily on Days 1-21, then 7 days off	
Cetuximab 	Pretreatment for infusion-related reactions per local standard of care   e.g., 50 mg diphenhydramine, H2 blocker (ranitidine or famotidine) and dexamethasone (8-20 mg)  See section 5.3.2 for guidance on infusion-related reactions	Loading dose: 400 mg/m   Subsequent doses 250 mg/m 	IV, administered over 2 hours  IV, administered over 1 hour (± 15 minutes)	Once weekly, start with loading dose D1 of wk 1 then subsequent doses given D1 of wk 2 and beyond	4 weeks (28 days)

1. In general, a histamine receptor antagonist prior to cetuximab infusion is recommended to prevent hypersensitivity reactions. Corticosteroid premedication may also be given per local guidelines. If hypersensitivity ruled out after the first infusion, premedication(s) may be omitted if permitted per local guidelines.
2. In Southeast only, test for galactose-alpha-1,3-galactose IgE must be performed and must be negative to be eligible for cetuximab therapy.

## 5.3 Toxicities and Dosing Delays/Dose Modifications

### 5.3.1 Dose Reductions/Modifications for Palbociclib

#### Allowed Dose reductions

- Starting dose = 125 mg/day
- First dose reduction = 100 mg/day
- Second dose reduction = 75 mg/day\*

Discontinue palbociclib if further dose reduction is needed.

Dose Modification and Management – Hematologic Toxicities*	
NCI-CTCAE Grade	Dose Modifications
Grade 1 or 2	No dose adjustment required
Grade 3	
Day 1 of cycle: Withhold palbociclib, repeat CBC monitoring within 1 week. When recovered to Grade <math>\leq 2</math>, start the next cycle at the same dose.
 
Day 15 of first 2 cycles: If Grade 3 on Day 15, continue palbociclib at current dose to complete cycle and repeat CBC on Day 22. If Grade 4 on Day 22, see Grade 4 dose modification guidelines below.
 
Consider dose reduction in cases of prolonged (<math>>1</math> week) recovery from Grade 3 neutropenia or recurrent Grade 3 neutropenia on Day 1 of subsequent cycles.

Grade 3 neutropenia† with fever <math>\geq 38.5^{\circ}\text{C}</math> and/or infection	
At any time: Withhold palbociclib until recovery to Grade <math>\leq 2</math>. Resume at next lower dose.

Grade 4	
At any time: Withhold palbociclib until recovery to Grade <math>\leq 2</math>. Resume at next lower dose.

\*Table applies to all hematologic AEs except lymphopenia (unless associated with clinical events, eg, opportunistic infections).

† Absolute neutrophil count (ANC): Grade 1  $<\text{LLN}$  -  $1500/\text{mm}^3$ ; Grade 2: ANC  $1000 - <1500/\text{mm}^3$ , Grade 3 ANC  $500 - <1000/\text{mm}^3$ ; Grade 4: ANC  $<500/\text{mm}^3$

Dose Modification and Management –Non-hematologic Toxicities	
NCI-CTCAE Grade	Dose Modifications
Grade 1 or 2	No dose adjustment is required
Grade <math>\geq 3</math> non-hematologic toxicity (if persisting despite optimal medical treatment)	
Withhold palbociclib until symptoms resolve to:
 
 
• <math>\leq</math> Grade 1:
 
• <math>\leq</math> Grade 2: (if not considered safety risk for patient)
 
 
Resume at the next lower dose

Patients to be monitored for pulmonary symptoms indicative of ILD/pneumonitis (e.g. hypoxia, cough, dyspnea). In patients who have new or worsening respiratory symptoms and are suspected to have developed ILD/pneumonitis, interrupt palbociclib immediately and evaluate the patient. In patients diagnosed with severe ILD or pneumonitis, palbociclib is to be permanently discontinued.

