### 5.3.2 Dose Modifications/Delays for Cetuximab (Rash)

Severe Acneiform Rash	Cetuximab Dosing	Outcome	Dose modification
1 st occurrence	Delay infusion 1 to 2 weeks	Improvement	Continue 250 mg/m 
		No improvement	Discontinue Cetuximab
2 nd occurrence	Delay infusion 1 to 2 weeks	Improvement	Reduce to 200 mg/m 
		No improvement	Discontinue Cetuximab
3 rd occurrence	Delay infusion 1 to 2 weeks	Improvement	Reduce to 150 mg/m 
		No improvement	Discontinue Cetuximab
4 th occurrence		Discontinue Cetuximab	

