### **5.6 Duration of Therapy**

Treatment may continue until:

- Disease progression
- Inter-current illness that prevents further administration of treatment

- Unacceptable adverse event(s)
- Pregnancy
- Patient decides to withdraw from study treatment, **OR**
- General or specific changes in the patient's condition render the patient unacceptable for further treatment in the judgment of the investigator.
- Subject completes maximum number of treatment cycles allowed per protocol
- Subject is lost to follow up

It is anticipated that subjects will receive on average 4 to 6 months of study treatment.

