### Dosage and Administration:

Cetuximab will be administered on a weekly basis in this trial per the standard dosing regimen described below.

- The recommended initial dose is 400 mg/m^2 administered as a 120-minute IV infusion (maximum infusion rate 10 mg/min)
- The recommended subsequent weekly dose (all other infusions) is 250 mg/m^2 infused over 60 minutes (maximum infusion rate 10 mg/min) until disease progression or unacceptable toxicity

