#### **6.2.2 Adverse Events Associated With Cetuximab**

**Infusion reactions:** serious reactions, requiring medical intervention and immediate and permanent discontinuation of cetuximab included rapid onset of airway obstruction, hypotension, shock, loss of consciousness, myocardial infarction, and/or cardiac arrest. Approximately 90% of severe infusion reactions occurred with the first infusion despite premedication with antihistamines. See section 5.3.3 for management guidelines for infusion-related reactions.

**Cardiopulmonary arrest:** and/or sudden death occurred in 4 (2%) of 208 patients treated with radiation therapy and cetuximab.

**Pulmonary toxicity:** Interstitial lung disease, including 1 fatality, occurred in 4 of 1570 (<0.5%) patients receiving cetuximab in patients with CRC and head and neck cancer.

**Dermatologic toxicity:** including acneiform rash, skin drying and fissuring, paronychial inflammation, infectious sequelae (eg, aureus sepsis, abscess formation, cellulitis, blepharitis, conjunctivitis, etc.). See sections 5.3.2 for dose modification information. See sections 5.4.1 and Appendix 12.1 for skin toxicity prophylaxis and toxicity management guidelines.

Hypomagnesemia and electrolyte abnormalities: reported incidence in 55% of 365 patients receiving cetuximab for CRC and head and neck cancer, with 6-17% of patients experiencing grade 3 or grade 4 events.

Increased tumor progression, increased mortality or lack of benefit in patients with Ras-Mutant mCRC: Cetuximab is not indicated for use in patients with Ras-mutations of either K-ras, N-ras.

EGFR expression and response: in CRC patients response rate to cetuximab did not correlate with either the percentage of positive cells or the intensity of EGFR expression.

Patient Counseling Information:

Advise patients:

- To report signs and symptoms of infusion reactions such as fever, chills, or breathing problems
- Of the potential risks of using cetuximab during pregnancy or nursing and the need to use adequate contraception in both males and females during and for 6 months following the last dose of cetuximab
- That nursing is not recommended during, and for 2 months following the last dose of cetuximab
- To limit sun exposure (use sunscreen, wear hats) while receiving and for 2 months following the last dose of cetuximab

For additional details, please refer to the cetuximab package insert.

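### The ILD/pneumonitis rule in section 5.3.1 holds palbociclib only; no rule in section 5.3 holds weekly cetuximab while suspected ILD is worked up

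*Combined protocol and SAP*

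**What the plan says.** The ILD/pneumonitis paragraph closes section 5.3.1, which covers palbociclib dose changes. For a patient with new or worsening respiratory symptoms who is "suspected to have developed ILD/pneumonitis, interrupt palbociclib immediately and evaluate the patient", palbociclib is the only drug acted on. The same is true of the severe case: "In patients diagnosed with severe ILD or pneumonitis, palbociclib is to be permanently discontinued". The amendment summary says this guidance came from a letter by palbociclib's manufacturer.

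The other rules in section 5.3 are:

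- The non-hematologic toxicity table in 5.3.1, for grade 3 or worse: "Withhold palbociclib until symptoms resolve to" grade 1, or grade 2 if there is no safety risk.
- Section 5.3.2, the cetuximab modification section: severe acneiform rash only.
- Section 5.3.3: infusion-related reactions only.

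Section 6.2.2, under pulmonary toxicity of cetuximab, reports: "Interstitial lung disease, including 1 fatality, occurred in 4 of 1570" patients. Sections 5.2 and 6.2.1 schedule cetuximab once a week.

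**The concern.** The protocol itself links both study drugs to ILD. When ILD is suspected, it gives no reason to blame palbociclib rather than cetuximab. A site that follows section 5.3 as written stops one drug at once and has no instruction about the other, so a patient could receive the next weekly cetuximab infusion before the evaluation is finished.

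The dosing calendar makes this concrete. Palbociclib is taken on Days 1 to 21 of a 28-day cycle, and cetuximab is also due on Day 22 (sections 7.6.4, 7.6.8 and 7.6.12). If ILD is suspected at a Day 22 visit, palbociclib is already in its week off, so interrupting it changes nothing that week. The drug due that day is the one no rule holds.

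The stake is patient safety in a rare but potentially fatal event. The primary endpoint and its analysis are not at issue.

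**Working it through.** **Step 1. Does any rule require a cetuximab hold for suspected ILD?**

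| Provision | Trigger | Drug acted on | Requires a cetuximab hold for suspected ILD? |
|---|---|---|---|
| 5.3.1, ILD paragraph | Suspected or severe ILD/pneumonitis | Palbociclib | No |
| 5.3.1, non-hematologic table | Grade 3 or worse, persisting despite treatment | Palbociclib | No |
| 5.3.2 | Severe acneiform rash | Cetuximab | No |
| 5.3.3 | Infusion-related reaction | Cetuximab (all trial treatment at grade 3 or 4) | No. Lung infiltrates appear only as an example of what may follow a grade 3 infusion reaction |
| 5.6 | Unacceptable adverse event, intercurrent illness, investigator judgment | Study treatment | No. It ends treatment; it does not set a temporary hold |
| 6.2.1, dosing | Weekly "until disease progression or unacceptable toxicity" | Cetuximab | No. It is a stopping rule |
| 6.2.2 | Lists ILD as a toxicity | None | No. For rash and infusion reactions it points back to section 5.3; for ILD it does not |
| 4.2.10 | History of ILD or pneumonitis | None (exclusion) | No. It lowers baseline risk and sets no on-treatment rule |

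No row supplies the hold.

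**Step 2. How often might cetuximab ILD arise? (context only)**

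Inputs: 4 cases in 1570 patients (section 6.2.2); 22 patients initially and up to 47 evaluable if both cohorts pass stage 1 (section 5.1).

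Rate: p = 4/1570 = 0.0025 = 0.25%, which agrees with the protocol's own statement of below 0.5%. The exact (Clopper-Pearson) 95% confidence interval is 0.07% to 0.65% (limits 0.000695 and 0.006510).

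Expected cases = n × p. Chance of at least one case = 1 − (1 − p)^n.

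| n | p | Expected cases | Chance of at least one |
|---|---|---|---|
| 22 | 0.000695 | 0.015 | 1.5% |
| 22 | 4/1570 | 0.056 | 5.5% |
| 22 | 0.006510 | 0.143 | 13.4% |
| 47 | 0.000695 | 0.033 | 3.2% |
| 47 | 4/1570 | 0.120 | 11.3% |
| 47 | 0.006510 | 0.306 | 26.4% |

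These are chances of any cetuximab ILD case. Harm from the gap would also need an investigator to go on infusing during the work-up, and the documents give no basis for that probability. They also give no ILD rate for palbociclib or the combination, and no rate for suspected ILD, which would be triggered by common symptoms such as cough or dyspnea.

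**The case against.** The strongest reply is that this is a drafting choice and that practice already covers it.

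- Section 5.1 has cetuximab given as standard of care. Section 6.2 calls it a commercial drug and refers to its prescribing information and package insert. Guidance on ILD may be there.
- The protocol does not write a cetuximab dose rule for every toxicity. Hypomagnesemia and electrolyte disturbance are far more frequent (55% of 365 patients, 6 to 17% at grade 3 or 4) and are handled by monitoring and repletion alone.
- Nothing tells a site to continue cetuximab. The ILD paragraph requires evaluation, study visits have a window of plus or minus 3 days (section 7.4, footnote 2), and sections 10.5 and 10.5.1 allow departures in an emergency or to remove an immediate hazard. A physician who stops one drug for suspected ILD is unlikely to infuse another that is listed as causing it.
- A mandatory hold would apply to every suspected case. Their number is unknown, so the total of missed doses cannot be bounded.

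Much of this stands, and it is why the point is minor. It does not close the gap. Each provision permits a delay or a stop, and none requires a hold on suspicion. The label's content is not in the documents. Outside emergencies, section 10.5 wants the study run exactly as the protocol describes, which favours an explicit rule over an inferred one. A sensible investigator might equally have stopped palbociclib unprompted, yet that rule was thought worth writing down.

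**Conclusion.** The concern holds as a narrow gap. The ILD rule covers one of the two drugs that the protocol links to ILD, and no protocol text requires cetuximab to be held while ILD is only suspected. For severe ILD, the general stopping provisions would ordinarily end cetuximab, so there the defect is only that the drug is not named. The palbociclib-only wording is explained by its source and is not an instruction to continue cetuximab.

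The improvement is small and inexpensive. The incidence figures (5.5% for 22 patients, range 1.5% to 13.4%; 11% for 47, range 3% to 26%) assume that the section 6.2.2 rate, from a mixed colorectal and head-and-neck population, carries over to this trial. The exclusion of prior ILD may lower it. The conclusion rests on the text and does not depend on these figures. Sample size, power and the Simon stopping rules are unaffected.

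**What to change.** Reword the ILD paragraph in section 5.3.1 so that it names both drugs, for example: *If new or worsening respiratory symptoms raise suspicion of ILD or pneumonitis, hold both palbociclib and cetuximab at once and evaluate the patient. If severe ILD or pneumonitis is diagnosed, stop both drugs permanently.* Add one ILD line to section 5.3.2 that refers to this paragraph.

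Whether and how to restart after confirmed non-severe ILD is a clinical decision for the sponsor; the documents do not settle it. The sponsor's clinicians should also confirm the permanent stop of both drugs in severe cases.

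The cost is one revised paragraph and one added line, by amendment with IRB approval. There are no extra visits, procedures or patients. The downside is a missed or delayed cetuximab dose, one infusion per week of work-up, in patients whose ILD is later ruled out. The rash table in section 5.3.2 already accepts a comparable interruption ("Delay infusion 1 to 2 weeks"), although for a diagnosed toxicity rather than a suspected one.
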